9.1.4 Final Follow up Visit / Visit 7 (3-6 months from Visit 5)

1. Subject to complete self-assessment of glabellar line severity at max frown using the Static 4-point Categorical Scale. See [7.3](#) and [Appendix 3](#).
2. Subject to complete the Subject Satisfaction Questionnaire. See [Appendix 1](#).
3. Physician to complete assessment of the subject's glabellar line severity at rest and max frown
CCI [REDACTED]
4. Physician to complete the CCI [REDACTED] See [Appendix 2](#).
5. Physician or designee will ask the subject about reactions, and document in accordance with the physician's real clinical practice.
6. Exit the subject from the study.

10 STATISTICAL METHODS PLANNED

10.1 Statistical and Analytical Plans

A Statistical Analysis Plan (SAP) will be developed as a separate document. The SAP will contain a more detailed and technical description of specific data conventions, calculations and of statistical procedures for executing the analyses that are specified in the sections of the clinical study protocol below. The SAP will be finalized prior to FSFV.

Any change made to the finalized SAP will be documented in the Clinical Study Report (CSR).

10.1.1 Data Transformations

Not applicable.

10.1.2 Populations Analyzed and Evaluability

The primary analysis will be performed on the enrolled population. Analysis on the per-protocol (PP) population maybe performed, if needed.

The rules for the allocation of subjects to each of the analysis populations will be defined and documented during a data review meeting held prior to database lock.

During the data review meeting, based on minor or major protocol deviations recorded, subjects may be excluded from the PP population.

Subjects may be excluded from the analyses if one or more of the following deviations occur.

- Subject did not complete the study
- Violation of inclusion/exclusion criteria

10.1.2.1 *Enrolled Population*

The enrolled population includes all subjects who are enrolled in the study treated at least once with *Dysport*.

10.1.2.2 *Per-protocol (PP) Population*

The Per Protocol (PP) population is a subset of the enrolled subjects who have no major protocol deviations, as outlined above.

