10.1.5 Subgroup Analysis

Subgroup analysis may be performed as determined and identified during the data review meeting.

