4.4. Prior/Concomitant Medication

The information of prior/concomitant medication including drug name, dose, unit, frequency, route of administration, start date, end date, ongoing, and reason for usage will be recorded in CRF.

4.5.Prior/Concomitant Treatment

The information of prior/concomitant treatment including name of treatment, start date, end date, ongoing, and treatment reason will be recorded in CRF during the study.

4.6.Protocol Deviation

Clinical operation team shall record the cause, date and severity of all protocol deviations in the file Protocol Deviation Tracking Log.

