6. ANALYSIS SETS

6.1.Full Analysis Set (FAS)

All subjects screened, enrolled in the study treated at least once with Dysport.

6.2.Per Protocol Set (PPS)

A subset of FAS that include subjects who have evaluable primary efficacy endpoints, have overall good compliance, and have no major protocol deviations during the study. Subjects excluded from PPS will be determined in Data Review Meeting before Data Base Lock.

6.3.Safety Set (SS)

The set of subjects who have received at least one dose of study treatment and for whom actual data on safety endpoints are available.

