7.1.1. Application of Analysis Sets

Baseline analyses will be based on FAS and PPS; efficacy analyses will be primarily based on PPS, and on FAS as reference; safety analyses will be based on SS.

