7.1.5. Significance Level

Statistical analysis will be performed with a two-sided test at a significance level of 5% whenever required.

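### The SAP puts the per-protocol set ahead of the protocol's enrolled population without listing the change, and part of that set's membership is left to a data review meeting with no stated masking of outcomes

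*Protocol*

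**What the plan says.** **Which set leads.** Protocol 10.1.2 assigns the primary analysis to the enrolled population and treats a per-protocol (PP) analysis as something to add if needed. SAP 7.1.1 reverses the order: "efficacy analyses will be primarily based on PPS, and on FAS as reference". SAP 7.4.1 then plans the primary endpoint on both sets.

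**Who is in the per-protocol set.** Protocol 10.1.2 says "The rules for the allocation of subjects to each of the analysis populations will be defined and documented during a data review meeting", to be held before database lock. It adds that, "based on minor or major protocol deviations recorded, subjects may be excluded from the PP population". Protocol 10.1.2.2 describes the same population as a "subset of the enrolled subjects who have no major protocol deviations, as outlined above". SAP 6.2 requires an evaluable primary endpoint, overall good compliance and no major deviation, and ends: "Subjects excluded from PPS will be determined in Data Review Meeting before Data Base Lock".

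**Who grades deviations.** SAP 4.6: "Clinical operation team shall record the cause, date and severity of all protocol deviations".

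**Subgroups.** Protocol 10.1.5: "Subgroup analysis may be performed as determined and identified during the data review meeting". None is named in the visible text of either document.

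**The concern.** A data review meeting before lock guards against bias when the people who decide exclusions cannot see the outcomes. This is a single-arm, open study. Protocol 10.3 allows data to be analysed before completion, and neither document says that outcome data are withheld from those who grade deviations or attend the meeting.

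If the enrolled population led, as the protocol has it, the meeting could not move the headline figure: everyone treated at least once is in. Once the per-protocol set leads, each discretionary exclusion of a subject who answered at Visit 6 changes the leading satisfaction percentage. There is no hypothesis (SAP 5), so what is at stake is bias in a descriptive estimate and its interval, which are the study's main result.

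**Working it through.** **Step 1: is the change of leading set real and recorded?** The protocol's enrolled population and the SAP's full analysis set (FAS) both consist of enrolled subjects treated at least once with the product, so they are in practice the same set. The protocol calls it primary; SAP 7.1.1 calls it the reference. SAP 7.7 records two added interim analyses, the deletion of the adverse drug reaction definition and the rewording of the unexpected-reaction definition. It does not record the change of leading set.

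**Step 2: the exclusion grounds side by side.**

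| Place | Ground for exclusion |
|---|---|
| Protocol 10.1.2 | Minor or major deviations; also names non-completion and eligibility violations as possible reasons |
| Protocol 10.1.2.2 | Major deviations only |
| Protocol 10.1.3 | Depends on how serious the deviation is |
| SAP 6.2 | No evaluable primary endpoint, lack of good compliance (undefined), or a major deviation |

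The SAP does not define a major deviation. SAP 7.3.2 refers to predefined categories of major deviation but does not give them.

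**Step 3: what can separate the two sets on Question 17?** SAP 7.2 uses data as observed, and SAP 7.1.2 bases percentages on non-missing data. A subject with no Visit 6 answer therefore counts in neither percentage, and the evaluable-endpoint criterion removes no one who answered. The two percentages can differ only through the deviation and compliance criteria, which are the discretionary ones. For example, a subject who answers at Visit 6 but misses Visit 7 has not completed the study and may be dropped under protocol 10.1.2.

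**Step 4: what will the deciders have seen?** The documents do not say. The interim analyses follow Visits 2 and 4 (SAP 7.6). Question 17 of the subject questionnaire and Question 7 of the physician questionnaire are asked only at Visit 6 (protocol Appendices 1 and 2). The interims are therefore not planned to show either overall-satisfaction endpoint, although they could show earlier satisfaction answers and glabellar line (GL) grades.

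**Step 5: size.** The plan has no figure to reproduce: the 250 subjects do not come from a calculation (SAP 3.6), and no satisfaction or exclusion rate is given. The following inputs are assumed:
- n = 250 answers, i.e. every planned subject answers;
- S = 225 satisfied or very satisfied (90%), pooled for illustration only, because the endpoint reports four categories;
- D = 250 − 225 = 25 dissatisfied or very dissatisfied.

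Full set: 225/250 = 90.0%, exact (Clopper-Pearson) 95% CI 85.6 to 93.4%.

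*Moderate case:* k = 25 excluded (10%), dissatisfied subjects twice as likely to go. The exclusion rate among satisfied subjects is a = k/(S + 2D) = 25/(225 + 50) = 0.0909. Satisfied subjects remaining: 225 × (1 − 0.0909) = 204.5. Estimate: 204.5/225 = 90.9%.

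*Upper bound:* 12 excluded (12/250 = 4.8%), all dissatisfied: 225/238 = 94.5% (90.8 to 97.1%).

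*Lower bound:* 12 excluded, all satisfied: 213/238 = 89.5%.

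The same steps at other assumed rates:

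| Full set | 10% excluded, 2:1 | 12 excluded, lower to upper bound |
|---|---|---|
| 200/250 = 80.0% | 81.5% | 79.0% to 84.0% |
| 225/250 = 90.0% | 90.9% | 89.5% to 94.5% |
| 238/250 = 95.2% | 95.7% | 95.0% to 100% |

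**The case against.** The strongest reply has three parts. First, the study is descriptive and a pre-lock review of deviations is normal. Second, SAP 6.2 already gives criteria, so the set is not invented at the meeting. Third, the plan is transparent: the primary endpoint is reported on both sets (SAP 7.4.1), exclusions are counted with reasons and by site (SAP 7.3.3), and all deviations are listed by subject (SAP 7.3.2). A per-protocol figure that had drifted from the full-set figure would be visible.

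Much of this stands. The criteria are incomplete rather than absent, and selection would be detectable. But detection after the event is not prevention, and the unselected figure is the one labelled as reference.

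Three stronger readings are tempting, and the documents do not support them:
- *That exclusions will be made with all outcomes known.* The text neither grants nor bars access. Possible access is an inference from the open design and the absence of stated masking. SAP 4.6 likewise says only that severity is recorded, not what the recorders can see.
- *That the interim looks reveal the primary result.* As planned, they come before Question 17 is asked.
- *That meeting-chosen subgroups will be tested at 5%.* SAP 7.1.5 says "Statistical analysis will be performed with a two-sided test at a significance level of 5% whenever required", and SAP 7.1.4 lists between-group tests, but both are general provisions. Neither is tied to subgroups, and the visible efficacy plan gives only proportions with exact intervals. The supported point is narrower: a subgroup picked at the meeting is not pre-specified.

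**Conclusion.** The point holds in limited form. Two contradictions are plain from the text: the leading set differs between protocol 10.1.2 and SAP 7.1.1 without an entry in SAP 7.7, and protocol 10.1.2 admits minor deviations as grounds while 10.1.2.2 and SAP 6.2 do not. Together with an undefined compliance criterion and no stated masking, they leave room for outcome-related exclusion from the set that carries the headline. The documents do not show that this is intended.

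The likely effect is modest: about 1 percentage point (90.0% to 90.9%) in the moderate case. The 94.5% figure is an upper bound that needs every excluded subject to be dissatisfied. Both rest on assumed satisfaction and exclusion rates. The changes are cheap, and they should be made before Visit 6 answers are reviewed.

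**What to change.** 1. Reconcile the leading set. Either restore the enrolled population (FAS) as primary with the per-protocol set as supportive, or list the change in SAP 7.7 and justify it.
2. Delete the words *minor or* from protocol 10.1.2. In SAP 6.2, replace the compliance criterion with a fixed list of major deviations, set before Visit 6 answers are reviewed.
3. Classify deviations and decide exclusions on an extract that leaves out satisfaction answers and GL grades.
4. Label any subgroup chosen at the meeting as post hoc, and report it descriptively with counts and confidence intervals.

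The cost is some SAP wording, one protocol sentence, one masked extract and less freedom at the meeting. The first item alone, if the enrolled population is restored, removes the meeting's influence on the headline estimate.

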10.1.3 Withdrawals and Deviations

All withdrawn subjects will be listed individually, including at least subject number, date and reason for withdrawal, and last visit performed.

Subjects with CSP deviations will be listed individually, including subject number and observed deviation. Depending on the seriousness of the deviation, the subject might be excluded from the PP population, which shall be documented prior to database lock.

10.1.4 Statistical Methods

In general, efficacy, safety, and baseline characteristics variables will be presented using descriptive statistics and graphs, as appropriate. Continuous endpoints will be summarized using descriptive statistics (e.g., mean, median, standard deviation, minimum and maximum values). Categorical endpoints will be presented in frequency tables with number and percentage of observations for each level.

95% confidence intervals (CIs) will be calculated whenever appropriate.

10.1.5 Subgroup Analysis

Subgroup analysis may be performed as determined and identified during the data review meeting.

10.2 Sample Size Determination

The sample size of approximately 250 subjects is not based on a statistical calculation. The selected number of subjects is regarded as sufficient for an evaluation of the studied endpoints by using descriptive statistics.

10.3 Analysis

Since this is an open non-interventional study, available data may be analyzed prior to study completion.

11 TRAINING / MONITORING / DATA MANAGEMENT / QUALITY ASSURANCE

11.1 Personnel Training

Investigators (i.e., physicians) and other responsible persons should be listed together with their function on the signature and delegation log. Study staff shall provide a curriculum vitae or equivalent, as appropriate.

It is the responsibility of the Investigator to ensure that all personnel involved in the study are fully informed of all relevant aspects of the study, including detailed knowledge of and documented training in all procedures to be followed.

11.2 Clinical Monitoring

The conduct of the clinical study will be closely monitored by representatives of the Sponsor to verify adherence to the clinical study protocol, ICH-GCP guidelines, national regulations, and applicable SOPs.

The Investigator will allow the Contract Research Organization (CRO)/Sponsor's representatives, to have direct access to all clinical study records, eCRFs, corresponding subject medical records, product(s) dispensing records, and any other documents considered source documentation. Additionally, the CRO/Sponsor representative is to have access to the product storage area and clinical study facilities.

The Investigator also agrees to assist the representative if required.

11.3 Data Management

All data management procedures will be detailed in a Data Management Plan (DMP).

11.4 Quality Assurance / Audit / Inspection

The clinical study is conducted under the sponsorship of the Sponsor in compliance with the applicable international and local regulatory requirements, applicable ICH guidelines, and SOPs for clinical study conduct and monitoring from the Sponsor and/or the CRO.

Audits of clinical study centers may be conducted by the Sponsor/CRO representatives, and inspection may be performed by Regulatory Authority (RA) inspectorates or Independent Ethics Committees (IECs) before, during, or after the clinical study.

The Investigator will allow and assist the CRO/Sponsor's representatives, IECs and any regulatory agency to have direct access to all requested clinical study-related records.

For the audits performed by, or on behalf of, the Sponsor auditors, audit certificate(s) will be provided by Quality Assurance.

11.5 Changes in Clinical Study Conduct / Amendments

11.5.1 Clinical Study Conduct

With the exception of eliminating an immediate hazard to a subject, the Investigator should not deviate from the clinical study protocol or implement any changes without written approval from the Sponsor and prior review and documented approval/favorable opinion from the IEC of a protocol amendment.

Changes that involve only logistical or administrative changes to the clinical study protocol are authorized. The Investigator should document and explain any deviation from the clinical study protocol.

11.5.2 Amendments

The Sponsor may modify the clinical study protocol at any time for ethical, medical, or scientific reasons. Any amendments will be handled according to applicable local regulations.

The Sponsor does not have to notify non-substantial amendments to the competent authorities or the IEC. However, non-substantial amendments should be recorded and detailed in subsequent submissions e.g., in the subsequent notification of a substantial amendment.

12 ETHICS AND GENERAL CLINICAL TRIAL CONDUCT CONSIDERATIONS

12.1 Independent Ethics Committee (IEC)

This clinical study protocol and all amendments will be reviewed and approved by the appropriate IECs.

This CSP and all applicable amendments will be reviewed and approved by the appropriate IEC. It is the responsibility of the Investigator to obtain approval of the CSP/CSP amendment(s) from the IEC. The study shall not begin until the required favorable opinion from the IEC has been obtained. The Investigator shall file all correspondence with the IEC in the Investigator file and provide copies of IEC approvals to the Sponsor as required. Any additional requirements imposed by the IEC or RA shall be followed.

12.2 Ethical Conduct of the Clinical Study

This clinical study will be conducted in accordance with the protocol, the HELSINKI declaration (1964) and subsequent amendments, and the ICH GCP, and in compliance with applicable national regulatory requirements.

12.3 Subject Information and Consent

All subjects who participate in this clinical study are required to be fully informed about the clinical study in accordance with GCPs guidelines, federal regulations, and guidelines and in accordance with local requirements.

The ICF approved by an IEC, will be fully explained to the subject.

Prior to enrollment into the clinical study, the subject and the Investigator must sign and date the consent form(s). The Investigator is responsible for maintaining each subject's consent form(s) in the Investigator's site file and providing each subject with a copy of the signed and dated consent form(s).

12.4 Protection of Personal Data

The completion of the study involves the gathering and processing of Personal Data as specified in the Regulation (EU) 2016/679 on the protection of individuals with regard to the processing of personal data and on the free movement of such data. For the purposes of the study, Sponsor will be considered the Data Controller, and Investigator and Institution will both be considered Data Processors.

All processing of Personal Data must be carried out in accordance with national legislation concerning the protection of Personal Data. The Institution and Investigator are responsible for complying with all requirements pursuant to national legislation in the country in which the Institution and Investigator are located.

The Sponsor shall, to the extent feasible, protect study subject identifier information.

Effective date: 2021-06-28 08:30

The Institution and Investigator are jointly responsible for obtaining the appropriate informed consent of each subject for the processing of Personal Data required in order to complete the study. Such consent shall include the consent to the transfer of Personal Data to government authorities located in countries outside the China.

The Institution and Investigator are jointly responsible for providing sufficient information to all subjects to enable them to give their informed consent not only to the participation in the study, but also to the processing of Personal Data. Such information includes information regarding the purposes of the processing, the length of time during which Personal Data will be stored, the right of access to stored Personal Data and the right to correction or purging of incorrect or obsolete Personal Data. A subject may also withdraw his or her consent at any time. A subject who withdraws his or her consent to the processing of Personal Data must be considered to have withdrawn from the study but the data collected until the consent was withdrawn may be used in the statistical analyses.

Authorized representatives from the Sponsor or a RA may visit the study center to perform audits/inspections, including source data verification, i.e., comparing data in the subjects' medical records and the eCRF. Data and information shall be handled strictly confidential.

All collection, processing and analyses of protected health information, personal data or similar will be conducted in compliance with applicable local, national and international rules, regulations and guidelines.

12.5 Contractual Requirements

A contractual agreement will be signed between the CRO/Sponsor and each Investigator/Institution. This document will contain supplementary information, including financial terms, confidentiality, the clinical study schedule, third party responsibility, and publication rights.

12.6 Data Collection and Archiving

12.6.1 Data Collection

The Investigator must maintain all required records for all subjects. Data for this clinical study will be recorded in the subject's source documents and in the eCRFs provided by the Sponsor. All data should be recorded in the eCRFs completely and promptly.

12.6.2 Source Documentation

The eCRF is considered a data entry form and does not constitute the original (or source) medical records unless otherwise specified. Source documents are all documents used by the Investigator or hospital that relate to the subject's medical history, verifying the existence of the subject, the inclusion and exclusion criteria, and all records covering the subject's participation in the study. Source documents may include a subject's medical records, hospital charts, clinic charts, the physician's subject study files, as well as the results of diagnostic tests such as laboratory tests, electrocardiograms, etc.

The Investigator must keep accurate separate records (other than the eCRFs) of all subject visits, being sure to include all pertinent clinical study-related information. A statement should be made indicating that the subjects have been included in this clinical study and have provided signed written Informed Consent. All AEs must be thoroughly documented.

Source documents shall be made available for inspection by the monitor at each monitoring visit, as well as during audits and/or inspections.

12.6.3 Archives

All pertinent data, samples, photographs, correspondence, and reports, the original or amended clinical study protocol, and all other material relating to the clinical study will be maintained securely in Sponsor/CRO/Investigator/Institution archives for the legally required duration for archiving.

The Investigator/Institution should maintain the essential clinical study documents as specified in Section 8 of ICH-GCP, and according to the applicable regulatory requirements.

The Investigator/Institution should take measures to prevent accidental or premature destruction of these documents.

If the Investigator retires, relocates, or withdraws from the responsibility of keeping the clinical study records for any other reasons, custody must be transferred to a person who will accept the responsibility. The Sponsor/CRO must be notified in writing of the name and address of the new custodian.

